## 2.5. Treatment Assignment

Under Protocol Amendment 1 (Figure 1a), subjects are randomized 1:1 to Group A (CS) or Group B (IS), stratified accordingly to tumor bulk (largest lymphoid mass  $< 5$  cm vs.  $\geq 5$ cm) and disease response to last therapy (relapse vs. refractory).

Since Protocol Amendment 2 (Figure 1b), this is an open-label and single-arm phase 2 study that all new subjects will be enrolled and treated by IS dosing only. During the first 2 cycles, subjects will receive open-label ME-401 administered at 60 mg once daily. After completing 2 cycles of daily therapy, subjects will continue ME-401 administered at 60 mg daily for the first 7 days of every 28-day cycle (7 days on treatment and 21 days off treatment). Subjects who progress disease on IS dosing have the option to have their ME-401 dosing switched to CS dosing.

Since Protocol Amendment 2, the initial CS treatment arm was terminated, and switched to IS dosing. For CS Subjects from Protocol Amendment 1, those who already completed 2 initial cycles of therapy were switched to IS dosing once they complete the ongoing cycle; those who had not completed the first 2 cycles were switched to IS dosing after the first 2 cycles.

For subjects who experience toxicity during the first 2 cycles while receiving daily therapy with ME-401, dose interruption followed by a switch to the intermittent schedule daily dosing for the first 7 days of every 28-day cycle is allowed. Subjects who experience toxicities on the IS will be managed by the instructions for management of potential drug-related toxicity (Protocol Amendment 3, [Table 4](#)), which may include dose interruption or permanent discontinuation of ME-401.

## **2.6. Study Procedures and Flowchart**

All study assessments for procedures will be performed at the visits and time points outlined in the Schedule of Assessments ([Table 1](#)).

**Table 1: Schedule of Assessments (Amendment 4)**

Assessment/Procedure	Screening b	Cycle 1			Cycle 2		Cycle 3	Cycle 4		Cycle 5	Cycle 6		Cycle 7	Cycles 10, 13, 16, 19, 22, 25 d...	EOT/30-Day Safety Follow-up e	Post-Treatment Long-Term Follow-up
		1 c	8	15	1	15	1	1	7	1	1	7	1			
Day(s) of Cycle	-28 to -1	1 c	8	15	1	15	1	1	7	1	1	7	1	1	30 (± 3) days post last dose or treatment discontinuation	Every 3 Months
Study Day(s)	-28 to -1	1	8	15	29	43	57	85	91	113	141	147	169	253, 337, 421, 505, 589...		
Visit Window (days) a			±3	±3	±7	±7	±7	±7	±7	±7	±7	±7	±7	±7 a		
Informed consent form (ICF)	X															
Medical history f	X															
Physical examination	X	X			X		X	X		X	X		X	X	X	
Symptom-directed exam g			X	X		X										
Vital signs h	X	X	X	X	X	X	X	X		X	X		X	X	X	
Height	X															
Weight	X	X			X		X	X		X	X		X	X	X	
ECOG performance status	X	X			X		X	X		X	X		X	X	X	
Pregnancy test i	X	X			X		X	X		X	X		X	X	X	
HIV testing j	X															
Hepatitis B and C testing k	X															
Adverse events l		X	X	X	X	X	X	X		X	X		X	X	X	
Concomitant medication m	X	X	X	X	X	X	X	X		X	X		X	X	X	
ECG n	X	X					X				X			X	X	
CBC with differential o	X	X	X	X	X	X	X	X		X	X		X	X	X	
Serum chemistry p	X	X	X	X	X	X	X	X		X	X		X	X	X	
Coagulation q	X	X			X		X			X			X	X	X	
PCR test for CMV	X	X			X		X	X		X	X		X	X		
Urinalysis (Dipstick) r	X	X			X		X	X		X	X		X	X	X	

Assessment/Procedure	Screening b	Cycle 1			Cycle 2		Cycle 3	Cycle 4		Cycle 5	Cycle 6		Cycle 7	Cycles 10, 13, 16, 19, 22, 25 d ...	EOT/30-Day Safety Follow-up e	Post-Treatment Long-Term Follow-up
		1 c	8	15	1	15	1	1	7	1	1	7	1			
Day(s) of Cycle	-28 to -1	1 c	8	15	1	15	1	1	7	1	1	7	1	1	30 (± 3) days post last dose or treatment discontinuation	Every 3 Months
Study Day(s)	-28 to -1	1	8	15	29	43	57	85	91	113	141	147	169	253, 337, 421, 505, 589...		
Visit Window (days) a			±3	±3	±7	±7	±7	±7	±7	±7	±7	±7	±7	±7 a		
COVID-19 test s	X															
Issue and assess compliance diary t		X			X		X	X		X	X		X	X		
Dispense study drug u		X			X		X	X		X	X		X	X		
PK Sampling v		X		X w	X				X			X				
Echocardiogram or MUGA x	X														X	
Correlative immune study (pre-dose) y		X		X	X		X			X			X	X	X	
Opportunistic infection monitoring z		X			X		X	X		X	X		X	X	X	
Post-Treatment Follow-up procedures aa																X

Response Assessment bb,cc	Screening	Every 2 Months for the First 6 Months			Every 3 Months for the Next 12 Months (through 18 Months)				Every 6 Months Thereafter
		61	121	182	274	365	456	547	
Study Day		61	121	182	274	365	456	547	730, 912, 1095...
Visit Window (days)		±7	±7	±7	±7	±7	±7	±7	±14
CT neck/chest/abdomen/pelvis dd	X	X	X	X	X	X	X	X	X
FDG-PET scan ee	X		X			X			
Bone marrow biopsy/aspirate ff						X			
Endoscopy with biopsy gg						X			

Abbreviations: ALP = alkaline phosphatase; ALT = alanine aminotransferase; ANC = absolute neutrophil count; aPTT = activated partial thromboplastin time; AST = aspartate aminotransferase; BP = blood pressure; BUN = blood urea nitrogen; CBC = complete blood count; CMV = cytomegalovirus; CMR = complete metabolic response; CO2 = carbon dioxide; CR = complete response; CT = computed tomography; ECG = electrocardiogram; ECOG = Eastern Cooperative Oncology Group; EOT = end of treatment; FDG-PET = 18F-fluorodeoxyglucose positron emission tomography; HcT = hematocrit; HGB = hemoglobin; HIV = human immunodeficiency virus; HR = heart rate; ICF = informed consent form; INR = international normalized ratio; LDH = lactate dehydrogenase; MCH = mean corpuscular hemoglobin; MUGA = multigated acquisition scan; PCR = polymerase chain reaction; PK = pharmacokinetic; PT = prothrombin time; RBC = red blood cell; SOC = standard of care; WBC = white blood cell.

- a. **Study Assessment Day(s)** – There is ±3-day window allowable for each clinic visit for Cycle 1 Day 8 and Cycle 1 Day 15. For Cycles 2 through 25, the allowable window is ±7 days. After Cycle 25, the allowable window is ±1 month for each clinic visit and its associated assessments.
- b. **Screening** – Screening assessments are to be performed within 28 days prior to enrollment. Upon confirmation of meeting eligibility criteria, subjects should be treated within a reasonable time frame (within 5 days). If there are >7 days between screening laboratory assessments and expected Cycle 1 Day 1 dosing, then the laboratory assessments should be repeated and reviewed prior to the first dose of ME-401. Some tests performed prior to obtaining ICF (e.g., CT scan, bone marrow biopsy) may not need to be repeated for the study as long as they were performed within the allowed screening window.
- c. **Cycle 1 Day 1** – Physical examination need not be repeated on Cycle 1 Day 1 if performed within 7 days prior to start of treatment. Laboratory assessments (CBC with differential, serum chemistry, coagulation, urinalysis) need not be repeated on Cycle 1 Day 1 if performed within 7 days prior to start of treatment.
- d. **Cycle 25+** – Subjects who remain on study after 25 cycles (approximately 2 years) will visit the clinic every 3 months (±1 month), with a response assessment performed every 6 months as per standard of care.
- e. **EOT/30-Day Safety Follow-up** – Visit will be completed 30 (±3) days post last dose of study drug administration (or prior to starting a new treatment if urgent treatment is required) or from study drug discontinuation.
- f. If known, record in the medical history information on COVID-19 vaccination administered at any time prior to subject consent to participate in the study.
- g. **Symptom-directed exam** – Performed on Cycle 1 Day 8, Cycle 1 Day 15, and Cycle 2 Day 15, only as needed/indicated, based on interim history.
- h. **Vital signs** – BP, HR, temperature.
- i. **Pregnancy test** – The screening serum pregnancy test in females of childbearing potential must be completed within 28 days prior to Cycle 1 Day 1. Urine or serum pregnancy test must be performed on study Day 1. For women of childbearing potential, a monthly serum or urine pregnancy test will be conducted every dosing cycle and 30 days after discontinuation of dosing.
- j. **HIV testing** – HIV antibody is required.
- k. **Hepatitis B and C testing** – Hepatitis B core antibody, Hepatitis B surface antigen, and hepatitis C antibody are required. Hepatitis B PCR is required if hepatitis B core antibody and/or surface antigen is positive. Hepatitis C PCR is required if hepatitis C antibody is positive.
- l. **Adverse events** – Recorded from the time of the first dose of study drug on Cycle 1 Day 1 and continues until 30 days after the last dose of study drug or start of new anti-cancer treatment.
- m. **Concomitant medications** – Recorded from 28 days prior to Cycle 1 Day 1 until the EOT/30-Day Safety Follow-up visit, or start of new anti-cancer treatment. Please, record information about COVID-19 vaccination, if performed.

- n. **ECG** – 12-lead ECGs performed at screening; Cycle 1 Day 1 pre-dose (unless the Screening visit is within 3 days prior to Day 1); pre-dose on Day 1 of Cycles 3, 6, 13, 19, and 25, and every 6 months thereafter; at the EOT/30-Day Safety Follow-up visit, and as clinically indicated. ECGs should be performed pre-dose. For Cycle 1 Day 1 and Cycle 3 Day 1, ECGs should be taken pre-dose and at expected  $C_{max}$  (3–5 hours after dosing).
- o. **CBC with differential** – WBC, ANC, RBC, HGB, HcT, lymphocytes, eosinophils, monocytes, basophils, platelets, and MCH. Screening labs must be repeated if performed >7 days prior to Cycle 1 Day 1.
- p. **Serum chemistry** – Glucose, BUN or urea, creatinine, sodium, potassium, chloride, calcium, ALP, AST, ALT, total bilirubin, total protein, albumin, LDH, and phosphorous. Screening labs must be repeated if performed >7 days prior to Cycle 1 Day 1.
- q. **Coagulation** – aPTT, PT/INR. Screening labs must be repeated if performed >7 days prior to Cycle 1 Day 1.
- r. **Urinalysis** – Dipstick or urine test (pH, specific gravity, glucose, ketones, blood, and protein). Screening labs must be repeated if performed >7 days prior to Cycle 1 Day 1.
- s. **COVID-19 test results** – Please record COVID-19 test results in the AE CRF page, if positive.
- t. **Issue and Assess Compliance Diary** – Compliance diary to record daily study drug administration. Returned diaries are to be assessed for study product compliance. New compliance diary is to be issued with each dispensing of ME-401.
- u. **Dispense Study Drug** – Study drug is to be taken orally once a day on an empty stomach at least 1 hour prior to food intake or 2 hours after food intake at the same time each day. On days of PK sampling, instruct subjects to not take study drug until after the pre-dose PK sample is drawn. Compliance diary and count of returned capsules are performed on each day of dispensing study drug.
- v. **PK sampling** – Pre-dose PK samples are to be obtained within 1 hour before study drug administration on Cycle 1 Day 1, Cycle 2 Day 1, Cycle 4 Day 7, and Cycle 6 Day 7. Pre-dose PK samples collected after Cycle 1 Day 1 are to be obtained within  $\pm 60$  minutes of the scheduled time, which is based on the Cycle 1 Day 1 dosing time.
- w. **PK Sampling – Cycle 1 Day 15** – pre-dose and 3 hours ( $\pm 30$  min) post intake of study drug. Collect data regarding food and drink intake 4 hours prior to study drug intake.
- x. **Echocardiogram or MUGA** – Performed at screening, EOT/30-Day Safety Follow-up visit, and as clinically indicated. The same methodology (echocardiogram or MUGA) should be used throughout the study.
- y. **Correlative Sample Study** – US Sites only. Samples will be obtained pre-dose on Day 1 of Cycle 1, and then pre-dose on the following visits: Day 15 of Cycle 1; Day 1 of Cycles 2, 3, 5, 7, 10; then every 3 cycles thereafter; and at the EOT/30-Day Safety Follow-up visit. Fresh blood samples will be collected and shipped overnight to a central laboratory for analysis. Samples may be shipped only Monday to Thursday. Samples may not be shipped for delivery on weekends or holidays. If possible, a sample will also be obtained when a subject develops a late onset Grade 2 AE of diarrhea/colitis, rash/mucositis, transaminase elevation, or non-infectious pneumonitis, or when a subject discontinues study drug permanently for another reason. Samples will be collected at the first visit of the adverse event, at the time when treatment is held, and at the time when treatment is resumed.
- z. **Opportunistic Infection Monitoring** – Prior to start of every cycle of treatment with ME-401, monitoring will be conducted, and for subjects with identified risk factors and those who developed an OI while on study treatment, additional assessments should include: CD4 and CD8 count and ratio, c-reactive protein, blood cultures, any additional laboratory and diagnostic methods according to local SOC reported as unscheduled laboratory and diagnostic methods of assessment, radiological imaging (i.e., chest X-ray or CT scans). Note: Treatment of the OI that started while on study should be based on local SOC.
- aa. **Post-treatment Follow-up Procedures** – Every 3 months from the last dose of study drug to obtain data regarding changes in efficacy assessments, death or subsequent therapy based on standard of care assessments. Imaging tests to assess disease status will be performed at least once every 6 months or earlier as indicated per standard of care. Any AE that has not returned to baseline or Grade  $\leq 2$  should be followed until it has returned to baseline or better, the event is assessed as stable by the Investigator, the subject is lost to follow up, or the subject withdraws consent. Survival follow-up will continue for up to 3 years after the last subject is enrolled in the study.
- bb. **Response assessment** – Imaging scans, physical examination, bone marrow aspirate/biopsy (if applicable), and laboratory evaluation as appropriate for individual subjects.
- cc. **Response assessment at the EOT/30-Day Safety Follow-up visit** – Perform imaging test (CT scan or PET/CT scan) only if last imaging tests outside the window noted for CT scan or PET-CT.
- dd. **CT Scan** – CT of the neck, chest, abdomen, and pelvis must be obtained at screening (within 6 weeks prior to Cycle 1 Day 1). CT scans must be performed using IV contrast. For subjects who are intolerant to contrast agents, the CT scan will be performed with oral contrast or MRI scans will be used.
- ee. **PET/CT** – FDG-PET scan must be obtained at screening (within 6 weeks prior to Cycle 1 Day 1), as indicated, and to confirm CR/CMR. PET/CT imaging is no longer needed once a CMR has been achieved and a CT scan is an appropriate imaging test.
- ff. **Bone marrow biopsy/aspirate** – Bone marrow biopsy/aspirate is obtained at screening and to confirm CR if PET scans were not performed or were not evaluable to assess bone marrow involvement. In addition, it can be performed as clinically indicated at the discretion of the Investigator.

§§ **Endoscopy with biopsy** – For subjects with gastric MZL, endoscopy with biopsy to be performed to confirm CR.

### **3. ENDPOINTS**

#### **3.1. Primary Efficacy Endpoint**

The primary efficacy endpoint is ORR, defined as the proportion of subjects achieving the best response rating of CR or PR based on the Modified Lugano Classification (response criteria summarized in [Appendix 5](#) of Protocol Amendment 2), as determined by IRRC.

For both Primary Analysis and NDA Analysis for FL, ORR will include best response of PR and/or CR prior to first PD that is reported before the data cutoff date for FL Primary Analysis, among all patients in the Primary Efficacy Population in FL (PEP FL).

As supportive analyses for NDA Analysis for FL, ORR will be summarized by 1) including PR or CR achieved that is reported before the data cutoff date for NDA Analysis for FL, among all patients in the Primary Efficacy Population in FL; 2) including PR or CR achieved that is reported before the data cutoff date for NDA Analysis for FL, among all patients in the ITT FL Population.

Time to response will be assessed to provide supportive information for the primary endpoint of ORR. It is defined as the time from the first dose of study drug to the first objective response for the subjects who achieved best response of CR or PR.

#### **3.2. Secondary Efficacy Endpoints**

The analysis of secondary efficacy endpoints, DOR, CR rate, PFS, TTF, recapture of response, DORR will be performed accordingly to the disease assessment reported by the IRRC. Analysis of ORR, DOR, CR rate, PFS, TTF, recapture of response, DORR will also be performed using Investigator assessment of disease response. In addition, the overall survival will be analyzed. Recapture of analysis and DORR will only be summarized for the IS patients who switched back to CS after PD.

##### **3.2.1. Objective Response Rate (ORR) by Investigator**

ORR defined as the proportion of subjects achieving the best response rating of CR or PR based on the Lugano Classification, as determined by the Investigator.

##### **3.2.2. Duration of Response (DOR) and Duration of Recaptured Response (DORR)**

DOR is defined as time from first (CR or PR) response to the time of first PD (based on the Modified Lugano Response Criteria) or the date of death due to any cause (whichever occurs earlier).

For Primary Analysis and NDA Analysis for FL, DOR will be analyzed based on the patients who achieved PR or CR prior to first PD, that is reported before the data cutoff date for the FL Primary Analysis.

As a supportive analysis for NDA Analysis for FL, DOR will be analyzed based on all patients who achieved PR or CR prior to first PD, that is reported before the data cutoff date for the NDA Analysis for FL submission.

To evaluate the duration of response for subjects who had recapture of response on the CS dosing ([Section 3.2.6](#)), DORR is defined as the time from recapture of response (CR or PR) to the time of second PD or the date of death due to any cause (whichever occurs earlier).

Detailed censoring rules are specified in [Table 2](#) (FDA guidance [[FDA 2015](#)] and [[FDA 2018](#)]). In general, in primary analysis for DOR and analysis for DORR, subjects will be censored at the date of last adequate assessment with evidence of no progression by the IRRC, in the following situations:

- No progression nor death
- Discontinuation for any reason other than IRRC documented PD or death, including loss to follow-up, toxicity, withdrawal of consent, etc.
- Start of new anti-lymphoma treatment without evidence of IRRC documented PD
- Death or progression after two or more consecutive missed scheduled visits.

Supportive analysis for DOR will be conducted to evaluate the robustness of the primary analysis result for DOR, by considering all progressions and deaths as events per European Medicines Agency (EMA) guidance ([EMA 2013](#)), regardless of whether they occurred after initiating next anti-lymphoma treatment, after 2 or more consecutive missed scheduled assessments, or being reported as clinical (non-IRRC reviewed radiographic) progression ([Table 3](#)).

For subjects in IS dosing switching to the CS at PD, both DOR and DORR will be estimated.

**Table 2: Censoring Rules for the Primary Analysis of DOR and DORR**

Situation	Date of Event or Censoring	Outcome
Progression documented	Date of earliest assessment which revealed progression determined by the IRRC	Event
Death before first PD assessment	Date of death	Event
Death between adequate assessment visits	Date of death	Event
No progression, nor death	Date of last adequate assessment with evidence of no progression by the IRRC	Censored
Discontinuation for any reason other than documented PD or death	Date of last adequate assessment with evidence of no progression by the IRRC	Censored
Loss to follow-up	Date of last adequate assessment with evidence of no progression by the IRRC	Censored
Switching back to CS dosing schedule without evidence of PD by IRRC prior to switching	Date of last adequate assessment with evidence of no progression by the IRRC before switching back to the CS dosing schedule	Censored
New anti-lymphoma treatment started without evidence of PD by IRRC	Date of last adequate assessment with evidence of no progression by the IRRC before the start of new anti-lymphoma treatment	Censored
Death or progression after two or more consecutive missed scheduled visits	Date of last adequate assessment with evidence of no progression by the IRRC	Censored

**Table 3: Censoring Rules for the Supportive Analysis of DOR**

Situation	Date of Event or Censoring	Outcome
Progression documented	Date of earliest assessment which revealed progression determined by the IRRC	Event
Death before first PD assessment	Date of death	Event
Death between adequate assessment visits	Date of death	Event
No progression, nor death	Date of last adequate assessment with evidence of no progression by the IRRC	Censored
Treatment discontinuation for any reason other than documented PD or death	Date of last adequate assessment with evidence of no progression by the IRRC	Censored
Loss to follow-up	Date of last adequate assessment with evidence of no progression by the IRRC	Censored
Switching back to CS dosing schedule without evidence of PD by IRRC prior to switching *	Date of earliest assessment which revealed progression determined by the IRRC or death after switching to CS	Event
New anti-lymphoma treatment started *	Date of earliest assessment which revealed progression determined by the IRRC or death	Event
Death or progression after two or more consecutive missed scheduled visits *	Date of earliest assessment which revealed progression determined by the IRRC or death	Event
Investigator claim of clinical progression leading to treatment discontinuation *	Date of clinical progression	Event

\* Outcome definitions are different from primary analysis of DOR

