**Figure 1b: Study Schema (Protocol Amendments 2 and 3)**

Abbreviations: EOT = End of Treatment; FU = follow up; PD = progressive disease.

a Screening from Day -28 to Day -1.

b IS dosing schedule: 60 mg daily for the first 2 cycles (56 days) followed by 60 mg daily for 7 days of every 28-day cycle (7 days on / 21 days off treatment).

c Follow-up Period will include: 1) EOT/30-Day Safety Follow-up visit will occur 30 ( $\pm 3$ ) days from the last day of study drug treatment. 2) Efficacy Follow-up - for subjects who discontinue study treatment due to reasons other than disease progression or death, response follow up will occur until PD of the start of a new anti-cancer therapy. 3) Survival Follow-up visits will occur every 3 months until death, and will continue for up to 3 years after the last subject was enrolled in the study.

d Response assessments will be performed every 2 months ( $\pm 7$  days) for the first 6 months of therapy, every 3 months ( $\pm 7$  days) during the following 12 months, and every 6 months ( $\pm 14$  days) thereafter (starting with month 18).

Subjects who discontinue study drug will remain in the study with follow-up conducted every 3 months from the last dose of study drug to obtain post-treatment long-term follow-up information on disease status (i.e., change in disease response, progression), start of subsequent therapy, and survival (death). During this post-treatment follow-up phase, all subjects who discontinued treatment due to reasons other than PD must continue imaging tests to assess disease status, performed per the original protocol-defined schedule for disease/response assessment, or earlier if clinically indicated. Imaging test results will no longer be collected when a subject starts a new therapy or disease progression occurs and is documented in the post-treatment long-term follow-up phase. Survival follow-up will continue for up to 3 years after the last subject is enrolled in the study.

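### SAP 3.2.4 sends PFS to the supportive censoring table instead of the primary one, and Table 3's treatment-discontinuation row overlaps its Event rows with no stated precedence

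*SAP*

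**What the plan says.** **PFS.** SAP 3.2.4 states that PFS censoring follows the rules for the primary DOR analysis, with one exception for subjects lacking baseline or follow-up assessments, and then refers to Table 3. By its title, and in the SAP's List of Tables, Table 3 gives the supportive DOR rules. The primary rules are in Table 2.

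**Supportive DOR.** SAP 3.2.2 says this analysis checks the robustness of the primary DOR result "by considering all progressions and deaths as events per European Medicines Agency (EMA) guidance". It lists what no longer prevents an event from counting: a next anti-lymphoma treatment, two or more missed assessments, and clinical progression that is not an IRRC-reviewed radiographic progression. Stopping study drug is not on that list.

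**The rows.** Table 3 lists as Censored "Treatment discontinuation for any reason other than documented PD or death". The row has no asterisk; the asterisk footnote reads "Outcome definitions are different from primary analysis of DOR". The matching Table 2 row is "Discontinuation for any reason other than documented PD or death", and the bullet in 3.2.2 is "Discontinuation for any reason other than IRRC documented PD or death, including loss to follow-up, toxicity, withdrawal of consent, etc". Table 3 also has a starred Event row, "Investigator claim of clinical progression leading to treatment discontinuation".

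**Follow-up after a stop.** SAP 2.3 says "all subjects who discontinued treatment due to reasons other than PD must continue imaging tests to assess disease status", on the original schedule. Protocol 5.1 says the same, and adds that imaging results are no longer collected once new therapy starts or progression occurs. Footnote aa of the Schedule of Assessments, in both documents, gives a different post-treatment frequency: at least once every 6 months.

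**The concern.** The PFS sentence names one set of rules and points to another. A programmer who follows the table number turns some censored subjects into events and lets investigator-claimed clinical progressions into IRRC-assessed PFS. SAP Table 4 lists PFS among the selected critical secondary endpoints.

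The DOR issue is one of precedence. Because scans continue after a stop for toxicity or another non-PD reason, later IRRC progressions and deaths will be in the data. Table 3 offers two outcomes for the same subject and does not say which applies. If the Censored row prevailed, the supportive analysis would drop events that its stated purpose is to count. SAP 1.2 says the final DOR analysis is meant to support the NDA filing, so the event rule should be settled in writing.

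**Working it through.** **1. PFS: the two tables side by side**

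| Situation | Table 2 (primary) | Table 3 (supportive) |
|---|---|---|
| Switch to CS without IRRC PD | Censored | Event |
| New anti-lymphoma treatment | Censored | Event |
| PD or death after two or more missed visits | Censored | Event |
| Investigator-claimed clinical progression leading to a stop | no row | Event |
| Treatment discontinuation, other reasons | Censored | Censored |

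The first four rows are the starred ones. Following the table number in 3.2.4 instead of its words changes the outcome in each.

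**2. DOR: which subjects fit two rows of Table 3**

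- Stops for toxicity, later IRRC PD: the documented-progression row (Event) and the discontinuation row (Censored).
- Stops for toxicity, later dies: a death row (Event) and the discontinuation row (Censored).
- Stops for clinical progression without documented PD: the clinical-progression row (Event) and the discontinuation row (Censored). Every subject of this kind fits both.

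The missing asterisk does not settle it. It says that the two tables agree on this row, and they agree whether both count later events or both censor them.

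**3. Which reading the text favours**

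DOR in 3.2.2 runs to first PD or death from any cause, with no on-treatment condition. The documented-progression row has none either. In Table 2 the new-therapy row dates censoring at "Date of last adequate assessment with evidence of no progression by the IRRC before the start of new anti-lymphoma treatment", and the CS-switch row is limited in the same way; the discontinuation row has no such limit. SAP 7.2.2 reports types of censoring, so the row may only label stoppers who never progress. The literal reading also gives an odd result: PD after a stop plus new therapy counts, although scans are then no longer collected, while PD after a stop alone, where scans are required, does not. The benign reading is the likelier one, but it is not written down.

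**4. DOR: size of the ambiguity**

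Assumed inputs:
- Responders: 91 x 0.655 = 59.6, about 60.
- Exponential PD with median DOR 12 months; response at month 2; scans at months 2, 4, 6, 9, 12, 15 and 18.
- AE-stop rates from Phase 1b (Protocol 1.6.2.3 and 1.6.2.1), treating median follow-up as person-time. IS group: 2/(43 x 155/365.25) = 0.110 per year, and 1 - exp(-0.110) gives about 10%. Monotherapy: 5/(52 x 236.5/365.25) = 0.148 per year, about 14%.
- Off-drug PD hazard 0.5, 1 or 2 times the on-drug hazard. The documents give none.
- Standard error of a 12-month rate near 56%: sqrt(0.561 x 0.439/60) = 0.064, or 6.4 points.

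Simulated shift in the 12-month DOR rate, in points, at 10% / 14% stops (400,000 responders per scenario):

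| Reading | Hazard x0.5 | x1 | x2 |
|---|---|---|---|
| Row covers only subjects with no later event | 0 | 0 | 0 |
| All stoppers censored at last scan before the stop | -0.8 / -1.1 | 0.0 / 0.0 | +1.2 / +1.6 |
| Only PDs after a stop censored, at the clean scan before that PD | +1.1 / +1.5 | +1.6 / +2.3 | +2.5 / +3.6 |

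The third reading is the least natural. At equal hazard it loses 6.8% to 9.5% of 36 PDs, that is 2.4 to 3.4 events. The stop rates are imprecise: annualised exact intervals are 1% to 33% (IS) and 5% to 31% (monotherapy). The IS group appears to pool monotherapy and the rituximab combination (47 + 43 = 52 + 38 = 90), and the monotherapy group includes the 60, 120 and 180 mg escalation. At 33% stops and equal hazard, the two literal readings give 0.0 and +6.0. Scans are kept on the original schedule after a stop; the six-monthly schedule in footnote aa was not modelled.

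**5. PFS: what can and cannot be said**

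The documents give no rate for CS switches without IRRC PD, for missed scans or for clinical progression without IRRC PD. With assumed frequencies of 5% to 15% (switches and clinical progressions per 12 months) and a median PFS of 12 months, Table 3 minus Table 2 at 12 months is:
- CS switch: +0.1 to +0.4 at unchanged hazard, -0.4 to -1.2 if doubled, -1.0 to -3.1 if fourfold.
- Two consecutive missed scans: -0.5 to -1.6.
- Clinical progression: -2.5 to -7.5. This is essentially the assumed frequency times the assumed 50% PFS (0.05 x 0.5 = 0.025; 0.15 x 0.5 = 0.075), so it restates the input.

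The standard error at n = 91 is sqrt(0.25/91) = 0.052, or 5.2 points. These figures show direction only.

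**The case against.** The strongest defence is that Table 3 is shorthand and cannot be read one row at a time. Its new-therapy row is labelled an Event with no progression condition in the label; taken literally, a subject who starts new therapy and never progresses would be an event without a date. Read as a whole, with the DOR definition and the stated aim of counting every progression and death, the discontinuation row can only mean stoppers with no later event. On PFS, the sentence states the right rule in words and Table 3's title says it is supportive, so a careful programmer would notice the slip.

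Most of this stands. A reader might infer that the supportive DOR analysis cannot test sensitivity to censoring at treatment stops, or that Table 3 is simply wrong. The documents do not support either: both follow only from the literal reading, which the text disfavours.

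What does not fall away is that no precedence is stated, and that the list of relaxed situations in 3.2.2 omits treatment stops. The clinical-progression overlap also needs its own words, because such a subject may have no later IRRC PD or death and would still sit in the Censored row. As for PFS, a censoring reference is an operative instruction, and this one contradicts the sentence that contains it.

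**Conclusion.** The PFS reference in SAP 3.2.4 is wrong as written. The Table 3 discontinuation row is an internal inconsistency whose likely intent is benign.

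The effect on DOR is zero under the benign reading. Under the literal readings it is probably small, -1.1 to +3.6 points at 10% to 14% stops. That range rests on an assumed 12-month median, assumed off-drug hazards, weak Phase 1b stop rates and post-stop scans on the original schedule.

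The effect on PFS cannot be sized from the documents. A reader might take the -7.5 points above as an expected bias. It is not: it needs both an assumed 15% clinical-progression rate and programming from the wrong table.

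Nor do the documents support an inference that the primary DOR analysis must be redefined. Its Table 2 row and the 3.2.2 bullet leave the same question open, but the DOR definition already points to counting later events. DOR and PFS carry no hypothesis test, and the ORR test is unaffected. The change should be made, because it is cheap and removes a choice that would otherwise be made with open-label data in view.

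**What to change.** 1. **SAP 3.2.4:** replace the reference to Table 3 with Table 2.
2. **SAP Table 3, discontinuation row:** limit it to subjects *with no later IRRC PD or death and not covered by the clinical-progression row*. The row then remains as a censoring category for SAP 7.2.2.
3. **SAP Table 2, discontinuation row, and the second bullet in 3.2.2:** add *with no later IRRC PD or death*, subject to the existing new-therapy, CS-switch and missed-visit rows.

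The cost is wording only: one row in each table, one bullet and one table reference, with no new scans or data. DOR may read slightly shorter than if progressions after a stop had been censored.
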